Hamlet TRIAL

PROTOCOL

Full title: Multicenter randomized controlled trial of Doppler guided Hemorrhoid Artery Ligation (DGHAL) and mucopexy versus mucopexy alone in the treatment of grade III Hemorrhoids.

S

hort title: Hamlet (Hemorrhoids Artery Mucosal Ligation prospEctive Trial) trial.

Alternative title: Doppler-guided or non doppler-guided arterial ligation and mucopexy for third degree hemorrhoids? That is the question. The Hamlet (Hemorrhoids Artery Mucosal Ligation prospEctive Trial) trial.

Developed by Department of Emergency and Organ Transplantation (DETO), University of Bari,
Italy

Hamlet Trial Management Group

Surgery

[name], MD, [name]

Dept of Emergency and Organ Transplantation, University of Bari, Italy,
c/o Azienda Ospedaliero-Universitaria Policlinico di Bari, [name]
[contact] Mobile [contact]

[contact]

e-mail: [contact]

Randomization

Simple randomization will be centralized and carried out by assigning the 3 treatment options to consecutive computer generated random number obtained through the website http://www.randomizer.at

The randomization code will be obtained by contacting the number or the [contact]/ [name] or by the e-mail address [contact] or [contact].

Clinical queries during office hours should be directed to one of the clinical coordinators or to an appropriate member of the Hamlet Management Group

Data Monitoring and Ethics Committee

Clinical data monitoring will be carried out by [name]: Dept of Emergency and Organ transplantation, University of Bari e-mail: [contact] [contact]

Independent Ethics Committee of the Azienda Ospedaliero Universitaria Policlinico Consorziale Bari

[name]

[contact] [contact] e-mail: [contact]

Protocol approval n. 4555/2014

Trial Sponsor: University of Bari, Department of Emergency and Organ Transplantation, DETO,

Section of Surgery, Bari, Italy, [contact] - [name]

Clinicaltrial.gov ID number: Protocol version: 14/3/18

Hamlet Study Office

For general queries, supply of trial materials, and collection of data:

Trial Coordinator: [name], mobile [contact] – office [name] e-mail [contact]

Computing: [name], MD – mobile [contact] – e-mail: [contact]

CONTENTS

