1.4 Mucopexy

The addition of suture mucopexy to DGHAL has extended the indication of this technique to III degree hemorrhoids with encouraging results in terms of postoperative pain and complication and long term recurrences.

About 6 mucopexy with resorbable sutures are usually performed with this procedure starting from 2 o'clock in clockwise direction.

A RCT and some case series have cast doubts on the usefulness of making DGHAL, claiming that mucopexy alone can yield similar results and with less time (Aigner et al). However, these studies have some weak points including small sample size and use of different devices.

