2. STUDY HYPOTHESIS

The hypothesis of the study is that a simple mucopexy procedure by suture-fixation of anal cushion without the aim of a Doppler device, could be as effective as DGHAL and mucopexy to manage prolapsing grade III hemorrhoids.

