3. STUDY DESIGN

3.1 General Design

Prospective, multi-centre, parallel-arm randomized controlled equivalence trial. Eligible patients will be randomized to either mucopexy without Doppler guided artery ligation or mucopexy with doppler guided hemorroidal artery ligation.

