3.2.1 Primary

[figure not shown]
Primary aim of the Hamlet trial is to demonstrate that mucopexy without DGHAL for grade III haemorrhoids have equivalent recurrence rate at 1 year follow up of DGHAL with mucopexy procedure

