4.2 Operative protocol

Patients with symptomatic grade III haemorrhoids will enter the study if they fulfil the entry and exclusion criteria and after written informed consent. They will be randomized in 2 groups: DGHAL with mucopexy (group A) and DGHAL without mucopexy (group B).

A cleansing enemas will be performed early in the morning at least 2 h before the operation. Antibiotic prophylaxis was not considered.

General or epidural anaesthesia will be performed according to the patient or anaesthetist preferences.

A urinary catheter will be inserted in all patients and removed after few hours from the operation.

The patients will be placed in the lithotomy position.

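### Section 4.2 defines group B as DGHAL without mucopexy, the reverse of the mucopexy-without-DGHAL arm that the rest of the protocol describes

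*Protocol*

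**What the plan says.** Section 4.2 (Operative protocol) names the two groups: "They will be randomized in 2 groups: DGHAL with mucopexy (group A) and DGHAL without mucopexy (group B"). The letters A and B are tied to an operation nowhere else in the protocol.

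The comparison is stated differently in these places:

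- The full title sets DGHAL and mucopexy "versus mucopexy alone in the treatment of grade III Hemorrhoids".
- Section 2 (Study hypothesis) asks whether "a simple mucopexy procedure by suture-fixation of anal cushion without the aim of a Doppler device" works as well as DGHAL with mucopexy.
- Section 3.1 (General Design) randomises patients to "mucopexy without Doppler guided artery ligation or mucopexy with doppler guided hemorroidal artery ligation".
- Section 3.2.1 (Primary) aims to show that "mucopexy without DGHAL for grade III haemorrhoids have equivalent recurrence rate at 1 year follow up", compared with DGHAL plus mucopexy.
- Section 4.2.1.3 (Mucopexy) gives the clock positions for the mucopexy in the group operated on without Doppler.

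**The concern.** The definition in 4.2 removes the wrong component. The trial asks whether Doppler-guided ligation can be dropped while mucopexy is kept. The group B of 4.2 keeps the ligation and drops the mucopexy.

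Two things would be at stake if the sentence were followed.

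- **The question.** Comparing DGHAL with and without mucopexy estimates what mucopexy adds. It says nothing about what DGHAL adds, so it cannot serve the primary aim. Section 5.3 analyses patients as allocated, so anyone operated on under the literal definition would stay in group B in the main comparison.
- **The patients.** Section 1.4 states: "The addition of suture mucopexy to DGHAL has extended the indication of this technique to III degree hemorrhoids". Only grade III patients are enrolled (3.7.1). A literal group B would lose the component that the protocol's own background credits with making DGHAL suitable for them.

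The position of the sentence matters as well. It is in the operative section, where a surgeon would look for what each group receives, and not in background text.

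**Working it through.** The point is textual, so the check is to set the definitions of the second arm side by side.

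| Place in the protocol | Doppler-guided ligation in the second arm? | Mucopexy in the second arm? |
|---|---|---|
| Full title | No | Yes |
| 2 Study hypothesis | No | Yes |
| 3.1 General Design | No | Yes |
| 3.2.1 Primary | No | Yes |
| 4.2.1.3 Mucopexy | No | Yes |
| 4.2 Operative protocol | Yes | No |

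1. *Size of the disagreement.* The five other places agree with each other on both components. Section 4.2 disagrees with all five on both. This is a swap of the two terms and not a loose paraphrase.

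2. *Consistency within section 4.2.* As 4.2 defines them, both groups have DGHAL, so no group is free of Doppler. Its own subsection 4.2.1.3 then instructs a non-Doppler group. The two statements cannot both be right.

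3. *Support elsewhere for an arm of DGHAL without mucopexy.* There is none. The technique text in 4.2.1.2 and 4.2.1.3 runs from each ligation straight on into the mucopexy and does not describe stopping after the ligation.

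4. *Descriptions left out of the count.* The alternative title, "Doppler-guided or non doppler-guided arterial ligation and mucopexy for third degree hemorrhoids", keeps mucopexy and contrasts Doppler with no Doppler. It can also be read as arterial ligation in both arms, so it is not a clean statement of the intended arm and is not counted.

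5. *Effect on the stated figures.* Section 5.1 gives 100 per arm, from 90% success in both arms, a 15% limit, power 0.8 and type I error 0.05. None of these inputs refers to the group letters. Correcting the label changes none of them, so no recalculation applies.

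**The case against.** The strongest reply is that the intention is obvious and the slip harmless. Much of this stands.

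- Groups A and B are named only in that one sentence. The front matter has the randomisation code obtained centrally by telephone or e-mail, and nothing says that it is a letter which the surgeon decodes from 4.2.
- Section 4.2.1.3 works against the literal reading, since it places the mucopexy for the non-Doppler group.
- Section 3.5 requires surgeons experienced in DGHAL and mucopexy, and 3.4 requires the randomisation and both treatments to be explained to each patient. A reversed arm would probably be noticed.
- Section 5.3 also provides for a protocol-compliant population, so analysis as allocated is not the only view of the data.

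These points bear on how likely harm is. They do not make the sentence correct: a multicentre protocol should not need its title and hypothesis to overrule its operative definition of the arms.

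A reader might draw three stronger conclusions, and the document supports none of them.

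- *That all 100 group B patients would have the wrong operation.* This requires every site to follow the slip against the title, hypothesis, design, aim and technique text. It is a worst case and not an expected effect.
- *That a DGHAL-only arm was really planned*, because the front matter speaks of "assigning the 3 treatment options to consecutive computer generated random number". Section 4.2 itself states two groups, and no other text describes such an arm. The third option could equally come from the two DGHAL devices compared under 3.2.2. That number is a separate inconsistency, and the document does not settle it.
- *That the surgical detail of the non-Doppler mucopexy is wrong or missing.* The mucopexy in 4.2.1.3 can naturally be read as the one just described there. Whether a ligating stitch is left out is for the investigators to say.

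**Conclusion.** Wrong as written. Section 4.2 reverses both components of group B and conflicts with five clear statements of the same arm, one of them in its own subsection. The intended arm, mucopexy without DGHAL, can be recovered with confidence, so a drafting slip is by far the likeliest explanation.

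The size is one phrase, but it is the phrase that says which operation a randomised group receives. Followed literally, it gives a comparison that cannot address the primary aim. The conclusion rests only on the wording of the protocol. It does not assume that any site acted on the label, and it implies no change to the sample size or power.

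**What to change.** Reword the group definition in 4.2 so that group A receives DGHAL with mucopexy and group B receives mucopexy without DGHAL. Then confirm that the randomisation key and the site forms describe the two groups in the same words. Operation notes would need checking only if a key or form turns out to carry the reversed label.

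The cost is one phrase and a note to sites and ethics committees. No patients, visits, procedures or analyses are added.

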4.2.1 Technique

4.2.1.1 Devices:

THD device produced by THD SpA (Correggio, Italy), consists of a proctoscope equipped with a Doppler probe and a light source. The proctoscope model (THD SlideTM, THD SpA) has a sliding part comprising the operating window and Doppler probe for better proximal and distal movement without repositioning the proctoscope during mucopexy

AMI device, HAL-RAR – Haemorrhoidal Artery Ligation and Recto Anal Repair is produced by the A.M.I. – Agency for Medical Innovations, Austria. The device includes an illuminated proctoscope (RAR Flexi Probe) which is introduced into the rectum, then rotated slowly to search for arteries. This proctoscope is connected with a Doppler signal which indicates the position of the hemorrhoid arteries.

4.2.1.2 DGHAL

A lubricating gel is applied to the tip of the THD or the AMI device and, with the patient in the lithotomy position, the proctoscope is introduced into the anal canal. The terminal branches of the superior rectal artery are detected by the Doppler signal 2–3 cm above the dentate line. The tip of the instrument is gently tilted and the arteries are ligated with a figure-of-eight suture using 2 / 0 polyglycolic acid inserted using a special needle-holder through an aperture in the operating proctoscope.

4.2.1.3 Mucopexy

After the haemorrhoid artery ligation, the suture is continued with three to five sutures applied 5 mm apart, making sure that the last is at least 5 mm above the dentate line. The suture is then tied to create a hemorrhoidopexy. The procedure is repeated after all artery ligations (6 ligations).

In the NON doppler group the mucopexy will start at two o'clock and repeated at 4, 6 8, 10, 12, in clockwise direction.

4.3 Post-Operative Management

Postoperative care will be according to current standards as directed by the operative surgeon.

- Pain control will initially be provided using parenteral (intramuscular, intravenous or epidural) administration of narcotics or analgesics.
- bulking agents (psyllium) or osmotic laxatives will be prescribed in order to allow easy defecation

5. STATISTICAL ANALYSIS

5.1 Sample Size Determination:

A sample size calculation shows that 100 subjects per arm will suffice for accepting of the equivalent hypothesis with power of 0.8 and a type I error probability of 0.05, an equivalent limit of 15% and expected percentage of success in both control and experimental group of 90% (sample size calculated with R).

5.2 Statistical Methods:

Results will be expressed as either mean and standard deviation (SD) or frequency (percentage). Between-group comparisons will be performed using Student's t-test (normally distributed data) or Mann-WhitneyU test (skew data) for continuous variables or Chi-square test for categorical variables. All hypotheses will two-tails with p < 0.05 considered as statistically significant.

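### Does the sample size of 100 per arm fail to follow from its own inputs, and leave room for a tighter equivalence limit at no cost?

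*Protocol*

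**What the plan says.** Section 3.1 describes a "Prospective, multi-centre, parallel-arm randomized controlled equivalence trial". Section 3.2.1 makes recurrence at one year the primary comparison.

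Section 5.1 states that "100 subjects per arm will suffice for accepting of the equivalent hypothesis with power of 0.8 and a type I error probability of 0.05". The other inputs are "an equivalent limit of 15"% and "expected percentage of success in both control and experimental group of 90"%. The calculation is said to have been done in R. The section does not name the formula, say whether 0.05 applies to each one-sided test or is split between them, or mention a continuity correction or an allowance for loss to follow-up.

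Section 5.2 adds a general rule: "All hypotheses will two-tails with p < 0.05 considered as statistically significant".

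**The concern.** A reader who puts the listed inputs into the usual formula for two one-sided tests gets 69 per arm, well short of 100. Taking 0.025 per side gives 85, which still does not match. The power figure then seems wrong, since on the first reading 100 per arm gives about 94% and not 80%.

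Two consequences would be worth attention. The success criterion might be unclear, because 0.05 per side corresponds to a 90% confidence interval and 0.025 per side to a 95% interval. And the trial might be holding unused precision while its limit is wide: with 10% expected recurrence, a 15-point limit reaches to 25%. On that view the sponsor could take a limit of about 12.5 points with the same patients.

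**Working it through.** **Inputs (section 5.1).** Success p = 0.90 in both arms, so the true difference is 0; limit m = 0.15, read as percentage points; power 0.8; type I error 0.05. The alpha per side is not stated, so both 0.05 and 0.025 are carried through.

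**Reproducing 100.** For two one-sided tests with no true difference,

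n per arm = 2p(1−p)(z₁₋ₐ + z₁₋β/₂)² / m², where 2p(1−p) = 0.18, m² = 0.0225 and z₁₋β/₂ = z₀.₉₀ = 1.2816.

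- At 0.05 per side: 0.18 × (1.645 + 1.2816)² / 0.0225 = 68.5, so 69.
- At 0.025 per side: 0.18 × (1.960 + 1.2816)² / 0.0225 = 84.1, so 85.
- At 0.025 per side with the Fleiss continuity correction: (84.06/4) × [1 + √(1 + 4/(84.06 × 0.15))]² = 96.9, so 97.
- At 0.025 per side with a score (Farrington–Manning) test, by exact binomial enumeration: 94.
- At 0.025 per side, uncorrected, with an assumed 15% loss: 85/0.85 = 100.

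The first two lines do not give 100. The next two come close enough for 100 to be a rounded figure. The last gives it exactly, but only by assuming a loss rate that the protocol does not state.

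**Power with 100 evaluable per arm.** The standard error is √(0.18/100) = 0.04243, and power = 2Φ(0.15/0.04243 − z₁₋ₐ) − 1. The first row is this approximation; the others come from exact enumeration.

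| Method | 0.05 per side | 0.025 per side |
|---|---|---|
| Wald, approximation | 0.941 | 0.885 |
| Wald | 0.938 | 0.880 |
| Newcombe | 0.929 | 0.847 |
| Score | 0.924 | 0.845 |
| Wald, continuity-corrected | 0.895 | 0.818 |

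Every entry is above 0.8. The 94% figure is the most favourable cell.

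**What a tighter limit would cost.** The limit that has 80% power at 100 per arm is 0.04243 × (1.645 + 1.2816) = 0.124 at 0.05 per side, and 0.04243 × (1.960 + 1.2816) = 0.138 at 0.025 per side. With the continuity correction at 0.025 per side it is about 0.148, so almost nothing is gained.

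For a limit of 12.5 points, uncorrected:

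- 100 evaluable: power 0.81 (0.05 per side) or 0.68 (0.025 per side).
- 85 evaluable (assumed 15% loss, standard error √(0.18/85) = 0.04602): 0.72 or 0.55.

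For the planned 15 points with 85 evaluable, uncorrected: 0.89 or 0.81.

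**What the 15-point limit demands of the data.** Using the planning standard error, the observed difference must be below about 15 − 1.645 × 4.243 = 8.0 points at 0.05 per side, or 15 − 1.960 × 4.243 = 6.7 points at 0.025 per side. If recurrence truly were 25% against 10%, equivalence would be declared only with a probability of about the alpha per side.

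**The case for a change.** The strongest opposing argument concerns where 100 came from. A two-sided superiority test of 90% against 75%, at alpha 0.05 and power 0.8, gives (1.960 × √(2 × 0.825 × 0.175) + 0.8416 × √(0.09 + 0.1875))² / 0.0225 = 99.5, so exactly 100. None of the equivalence calculations gives exactly 100 without an unstated loss allowance. It is therefore possible that a superiority routine was used for an equivalence design. That coincidence stands, but it does not prove the source. Even if it is the source, the resulting number still meets the equivalence requirement in every cell of the table.

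The second argument is that the unstated alpha affects how much loss the trial can bear. This also stands in part. With an assumed 20% loss (80 evaluable), uncorrected power is 0.87 at 0.05 per side but 0.77 at 0.025 per side. With 85 evaluable at 0.025 per side, the score test gives 0.75 and the continuity-corrected test 0.71. The sufficiency claim therefore holds for evaluable patients and not under every combination of a strict test and heavy loss. But this argues against spending the reserve on a narrower limit; it does not show that 100 was miscalculated.

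The width of the limit is a clinical judgement. Nothing in the protocol contradicts 15 points, and the arithmetic does not decide it.

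**Conclusion.** The concern does not call for a change. Section 5.1 says that 100 per arm is enough for 80% power, and that is true under each equivalence method checked, at either alpha per side, provided that 100 per arm are evaluable and success is 90% in both arms. Under the two-tailed rule of section 5.2, the score and continuity-corrected calculations need 94 and 97, so 100 is a normal rounding. Any departure from the minimum is on the safe side: power from 0.82 to 0.94 against a stated 0.8.

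The apparent surplus is not free. It is the only cushion for loss before the one-year endpoint, and at 0.025 per side it is small. Moving to 12.5 points would trade it for power as low as 0.55 under an assumed 15% loss.

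What remains is that section 5.1 does not name the test, the alpha per side or a loss allowance, so 100 cannot be traced to one calculation. The formula and interval level are details that a statistical analysis plan commonly supplies, and none is shown here. Writing them down would help a reader but would alter neither the number of patients nor the limit.

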3.2.2 Secondary

- SAFETY: Demonstration that the new treatment will not add related morbidity
- Comparison of the outcome among the two devices (THD and AMI/ HAL-RAR) for DGHAL

_

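### The trial is designed for equivalence within 15 points, but its stated analysis is a two-sided chi-square test of difference, which cannot show equivalence

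*Protocol*

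**What the plan says.** Three places in the protocol commit the trial to equivalence. Section 3.1 describes the design as "Prospective, multi-centre, parallel-arm randomized controlled equivalence trial". Section 3.2.1 sets the primary aim: "to demonstrate that mucopexy without DGHAL for grade III haemorrhoids have equivalent recurrence rate at 1 year follow up". Section 5.1 states that "100 subjects per arm will suffice for accepting of the equivalent hypothesis", using "an equivalent limit of 15% and expected percentage of success in both control and experimental group of 90" per cent, a type I error of 0.05 and power of 0.8.

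Section 5.2 then gives the analysis. It names Student's t, Mann-Whitney and chi-square tests and ends: "or Chi-square test for categorical variables. All hypotheses will two-tails with p < 0.05 considered as statistically significant". One-year recurrence is categorical, so it falls under chi-square. The section mentions no confidence interval, no pair of one-sided tests and no exception for the primary endpoint. The 15% limit appears only in section 5.1.

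Section 3.2.2 adds a secondary aim: "SAFETY: Demonstration that the new treatment will not add related morbidity". No margin is given for it.

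**The concern.** An equivalence trial has to reject the null that the true difference is 15 points or more in either direction. Chi-square has the opposite null, that the difference is zero, and the limit does not enter it. Followed literally, section 5.2 leaves only two outcomes. A significant result shows a difference. A non-significant result shows nothing about the limit.

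The only route from that test to the stated aim is to treat p ≥ 0.05 as equivalence. That reading would not hold the 5% error rate stated in section 5.1. It would also reward lost data, because the fewer patients are followed, the easier non-significance becomes. The primary conclusion of the trial is therefore at stake.

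**Working it through.** **Inputs.** From section 5.1: 100 per arm, success 90% in both arms, limit 15% (read as absolute percentage points), type I error 0.05, power 0.8. From section 5.2: chi-square, two-sided, p < 0.05. Assumed here: 80, 85 or 90 analysable patients per arm, since the protocol states no dropout figure.

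**The stated sample size.** For equivalence by two one-sided tests, n per arm = 2p(1−p)(z₁₋α + z₁₋β/₂)²/δ².
- One-sided α = 0.05: 2 × 0.9 × 0.1 × (1.645 + 1.282)²/0.15² = 68.5, so 69 (82 with continuity correction).
- One-sided α = 0.025: 2 × 0.9 × 0.1 × (1.960 + 1.282)²/0.15² = 84.1, so 85 (97 with continuity correction).
- For comparison, the two-sided test-of-difference formula for 90% v 75% at 80% power gives exactly 100.

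The stated 100 is therefore close to one equivalence variant (97) and equal to the difference-test size. It covers either equivalence rule.

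**Error if non-significance is read as equivalence.** All 101 × 101 binomial outcomes were enumerated at 100 per arm, with the true difference set exactly at the limit. The first two result columns give the probability that chi-square is non-significant. The last gives the probability that the 90% Wald interval lies wholly within ±15 points.

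| True success | n per arm | Chi-square | With continuity correction | 90% interval rule |
|---|---|---|---|---|
| 90% v 75% | 100 | 18.4% | 24.8% | 5.4% |
| 90% v 75% | 90 | 23.3% | 29.2% | 5.4% |
| 90% v 75% | 85 | 25.2% | 32.5% | 5.3% |
| 90% v 75% | 80 | 28.4% | 36.1% | 5.6% |
| 85% v 70% | 100 | 27.1% | 33.2% | 5.2% |
| 95% v 80% | 100 | 7.9% | 12.8% | 6.0% |

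At the planned rate the inflation is 18.4/5 = 3.7 to 24.8/5 = 5.0 times. With the better arm at 95% it is 7.9/5 = 1.6 to 12.8/5 = 2.6 times.

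**Single tables where the two rules part** (Wald interval, d ± 1.645 × SE, uncorrected p unless stated):
- 90/100 v 81/100: p = 0.07. SE = √(0.90×0.10/100 + 0.81×0.19/100) = 0.0494, so the 90% interval is 0.9 to 17.1 points. Not significant, yet equivalence is not shown.
- 98/100 v 90/100: p = 0.017 (0.037 corrected). SE = √(0.98×0.02/100 + 0.90×0.10/100) = 0.0331, so the 90% interval is 2.6 to 13.4 points. Significant, yet within the limit.

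**Power of the interval rule** (true success 90% in both arms):
- 100 per arm: 93.8% with a 90% interval, 88.0% with a 95% interval.
- 85 per arm: 88.8% and 80.5%.
- 80 per arm: 87.0% and 76.8%.

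For the 95% interval at 100 per arm, false equivalence at 90% v 75% is 2.7%.

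**The case against.** The protocol never writes that a non-significant chi-square will count as equivalence, so the inflated error belongs to a reading and not to a stated rule. Section 5.2 is also a generic paragraph that does not name recurrence, and an unseen SAP may hold a proper interval rule. The first point stands as a condition on the error figures. The second does not remove the conflict. Section 5.2 is not silent: it fixes a two-tailed rule for every hypothesis. A SAP that followed it would repeat the fault, and one that used an interval rule would contradict the protocol.

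Three further limits stand:
- The inflation depends on the success rates. It is at least threefold at the planned 90% and larger at 85% v 70%, but only 1.6 to 2.6 times at 95% v 80%.
- A result can be both statistically different from zero and equivalent within a margin. The 98 v 90 table therefore shows that the two tests answer different questions; it is not an error of chi-square, and such tables would be uncommon at the planned rates.
- The safety aim has no margin, so no equivalence null for morbidity was ever specified. The logic is similar, but the point is secondary.

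**Conclusion.** The concern holds. The test fixed in section 5.2 does not address the primary hypothesis set in sections 3.1, 3.2.1 and 5.1, and this must be corrected because it decides the trial's main conclusion. That much needs no assumption beyond the protocol's own text.

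The size of the error rests on two conditions: that non-significance is taken as equivalence, and that the better arm succeeds at about the planned 90%. Under both, false equivalence at the limit is 18.4% to 24.8% with 100 per arm, and 25.2% to 32.5% with an assumed 85 per arm, against about 5% for the 90% interval rule.

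**What to change.** In section 5.2, state that 1-year recurrence is analysed by the difference in proportions between arms with its confidence interval, and that equivalence is concluded only if the whole interval lies between −15 and +15 percentage points. Say which level applies: a 90% interval (two one-sided tests at 5%) or a 95% interval (2.5% per side). Restrict the two-tailed p < 0.05 rule and chi-square to secondary comparisons. Report morbidity as a difference with its confidence interval, and do not claim absence of added morbidity from p > 0.05.

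The cost is an amendment to the protocol wording, and to the SAP if it follows section 5.2. No more patients or data are needed: the stated 100 per arm exceeds 80% power under either interval, and an assumed 85 analysable per arm still does.
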